### 3.10.3. Daily Hunger

For analyses of the daily hunger score questionnaire in patients  $\geq 12$  years of age, MI will be used to model missing measurements at the primary timepoint. The methods outlined above for

weight will be utilized for the daily hunger score questionnaire. The multiple imputation will function at the weekly average of daily hunger score level and not at the daily level scores.

MI approach for the daily hunger score questionnaire will be independent of the MI approach for weight; that is, while we would expect similar missingness between weight and daily hunger questionnaire domains, alternate approaches are acceptable. For example, if RD approach does not converge for weight and therefore wash-out imputation is used for weight, but RD approach does converge for daily hunger score, then RD approach will be used for hunger score even if “alternate” in approach to weight.

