-  All blood pressure (BP) and heart rate (HR) measurements are to be obtained with the patient in the sitting position following at least 5 minutes of rest. All measurements will be taken in triplicate, approximately 2 minutes apart. When possible, BP should be taken in the non-dominant arm throughout the trial, using the same methodology (automated or manual). Body temperature ( $^{\circ}\text{C}$ ) and respiration rate (breaths/minute) will be obtained in the sitting position following at least 5 minutes of rest. Repeat measures and more frequent monitoring can be implemented for significant increases in BP or HR.

-  At Screening, a single 12-lead ECG will be performed in the supine position following a period of at least 10 minutes of rest. See Section 6.8.5.
-  A urine pregnancy test may be performed to expedite availability of results prior to dosing on Day 1. All in-clinic pregnancy tests per SoA will be serum tests; dosing may continue with results pending. At telehealth visits, urine pregnancy tests will be performed using pregnancy test kits. Additional pregnancy tests may be required according to local regulations and/or requirements.
-  See Section 6.8.6 for FSH screening requirements.
-  IGF1 labs will be drawn at Baseline and approximately every 3 months for patients taking growth hormones.
-  Safety laboratory tests will be performed per Section 6.8.6 before the morning meal (fasted).
-  Blood samples will be collected prior to dose administration for CCI [REDACTED]
-  See Section 6.6.4. Hunger Questionnaires and Symptoms of Hyperphagia Questionnaire will be recorded during the trial using an at-home e-diary as follows: during the Screening Period for 7 consecutive days before the enrollment visit (Day 1) for 7 consecutive days before each scheduled trial visit, scheduled telehealth visit, or at the ETT visit as applicable. These questionnaires should be completed prior to the morning meal (fasted) before dosing and at home using the e-diary. CCI [REDACTED]

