**3.11.1. Therapeutic Dose Start Date and Primary Timepoint**

Efficacy data will be summarized formally at the primary timepoint, after 52 weeks on therapeutic dose.

Setmelanotide or placebo equivalent will be administered at starting doses in all patients and subsequently up-titrated towards the target therapeutic dose, CCI dependent. CCI

[REDACTED]

[REDACTED]

[REDACTED]

[REDACTED]

CCI  
.

To identify the primary timepoint, the following steps will be utilized:

- Calculate the number of days from therapeutic dose start date for all on-site visits excluding bridging visits
- The non-missing, on-site visit occurring closest to day 365 within a window of 305 to 425 days from therapeutic dose start date will be selected
- If multiple results are equidistant from Day 365 (from the therapeutic dose start date), the latest of these equidistant results is selected
- If no results have been reported within days 305 to 425 from therapeutic dose start date, then the primary timepoint is considered missing

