3.11.2. Efficacy Windowing for Patients

As noted in Section 3.10.2, RD MI and washout MI methodologies will impute based on results from baseline, Visit 2, Visit 4, Visit 7, Visit 9, Visit 11, and the primary timepoint. To ensure that captured data is used to the greatest extent possible, expanded windows as compared to the SOA will be considered. Note that visit windowing and use of on-site additional, unscheduled, or early termination visits will only occur if the specific visit as recorded and tabulated per the CRF is missing. That is, for on-site Visits 2, 4, 7, 9, and 11, the value collected directly from the CRF will be used, regardless of timing of that visit. If there is no collected value for a given visit per the CRF, the missing value will be replaced from other, non-missing, on-site visits (excluding bridging visits) based on the target analysis windows outlined in Table 3-1. Similar to primary timepoint handling, if there are multiple records equidistant from the target day, the latest of the equidistant records will be utilized.

Table 3-1 Efficacy Windowing for MI Models

Visit	Visit 2	Visit 4	Visit 7	Visit 9	Visit 11
SoA Target Visit Day	22	78	162	218	274
Target Analysis Visit Window	14, 50	51, 120	121, 190	191, 246	247, 304

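### The on-site-visit rule written for weight also governs the home hunger diary, so an observed diary week before a telehealth Week 52 visit cannot stand in when no on-site week is evaluable

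*SAP*

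**What the plan says.** SAP 3.10.3 handles missing hunger scores in patients aged 12 or older by carrying over the plan for body weight: the methods given for "weight will be utilized for the daily hunger score questionnaire". The adaptation it states is the level of imputation: "The multiple imputation will function at the weekly average of daily hunger score level and not at the daily level scores".

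SAP 3.11.1 defines the primary timepoint, and its opening sentence is not confined to weight: "Efficacy data will be summarized formally at the primary timepoint, after 52 weeks on therapeutic dose". The first step reads "Calculate the number of days from therapeutic dose start date for all on-site visits excluding bridging visits". The second selects "The non-missing, on-site visit occurring closest to day 365 within a window of 305 to 425 days from therapeutic dose start date". If nothing qualifies, "then the primary timepoint is considered missing".

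SAP 3.11.2 covers the intermediate visits that feed both imputation methods (Visits 2, 4, 7, 9 and 11). Where a visit's own value is absent, "the missing value will be replaced from other, non-missing, on-site visits (excluding bridging visits", using the windows in Table 3-1.

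Protocol Table 1, footnote 17, has the hunger and hyperphagia diaries completed at home "for 7 consecutive days before each scheduled trial visit, scheduled telehealth visit, or at the ETT visit as applicable". The telehealth footnote to the same table lets seven visits (Weeks 8, 16, 20, 28, 36, 44 and 52) be held remotely. It waives height, weight, waist circumference and vital signs at those visits, but not hunger.

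**The concern.** The visit-type filter has a reason for weight: the value exists only if the patient stood on the clinic scale. For hunger it has none. The diary is filled in at home in the same way whether the visit that follows is in clinic or by telehealth, yet the week counts in the first case and not in the second. The investigator chooses the location after randomisation, and the choice says nothing about the quality of the diary.

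This sits badly with the SAP's own aims. Section 3.11.2 widens the windows so that as much captured data as possible is used. Section 4.3.5.3 calls a diary week evaluable with a single daily entry, so one entry before a clinic visit is usable while seven before a telehealth visit are not. The treatment-policy strategy in 4.3.1 includes every collected measurement, and 4.3.5 says hunger follows the same methodology.

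At stake are the third key secondary endpoint and the 2-point hunger responder endpoint, which uses the same imputed data (SAP 4.3.6.1). If the wash-out fallback is used, a setmelanotide patient's discarded week is replaced by a draw based on placebo data and that patient's baseline alone (SAP 3.10.2).

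**Working it through.** **The plan's own figure.** The plan gives no power or missing-data figure for hunger. Its one power figure, about 99.5% for BMI, reproduces: 80 and 40 less 20% dropout leave 64 and 32; the noncentrality is 10 / (10 × √(1/64 + 1/32)) = 4.62 on 94 df; power at two-sided 0.05 is 0.9955. This does not bear on the present point.

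**Inputs.** Visit days are from Protocol Table 1. The primary window (305 to 425 days from therapeutic start, target 365) is from SAP 3.11.1. The substitution windows are from SAP Table 3-1. The definition of therapeutic start is redacted. I place it at about Day 22 to Day 50 because 52 weeks is 364 days, and the End of Treatment columns fall on Days 386 (V15) and 414 (V16): 386 − 364 = 22 and 414 − 364 = 50.

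**Step 1: which telehealth-eligible visit can supply the endpoint?** Day 358 minus start is at least 305 for any start up to Day 53, so Week 52 (V14) qualifies across the assumed range. The next latest, Week 44 (Day 302), is 302 − 22 = 280 days out even for a Day 22 start. Only V14 is in play.

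**Step 2: which on-site visits already lie in the window?** Days from therapeutic start are:

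| Start | V13 (Day 330) | V14 (Day 358, telehealth-eligible) | V15 (Day 386) | V16 (Day 414) |
|---|---|---|---|---|
| Day 22 | 308 | 336 | 364 | 392, if attended |
| Day 25 | 305 | 333 | 361 | 389, if attended |
| Day 26 | outside | 332 | 360 | 388, if attended |
| Day 50 | outside | 308 | 336 | 364 |

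A Day 22 start with End of Treatment at V15 has two on-site visits in the window (V13, V15). A Day 50 start with End of Treatment at V16 also has two (V15, V16). A start after Day 25 that ends at V15 has one. V14 is used only if none of these, and no on-site unscheduled or early termination visit in the window, has an evaluable week.

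**Step 3: would admitting V14 change anyone else's value?** For starts from Day 22 to Day 50, V14 lies 29 to 57 days from day 365 and V15 lies 1 to 29 days from it, with V15 the nearer at every start. On scheduled days V14 would act only as a fallback.

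**Step 4: Table 3-1.**

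| Model visit | Window | Scheduled telehealth-eligible days inside |
|---|---|---|
| V2 | 14–50 | 50 |
| V4 | 51–120 | 106 |
| V7 | 121–190 | 134, 190 |
| V9 | 191–246 | 246 |
| V11 | 247–304 | 302 |

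Each window holds one scheduled visit that is always in clinic, the model visit itself. If its diary week is missing there is no scheduled fallback unless a telehealth-eligible visit was held on site.

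**Step 5: illustrative size (assumptions, not document figures).** Suppose each diary week is missing independently with probability q, and V14 is by telehealth. The share of patients whose endpoint would be observed at V14 instead of imputed is q(1 − q) with one on-site visit in the window and q²(1 − q) with two.

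| q | One on-site visit | Two on-site visits |
|---|---|---|
| 5% | 4.8% | 0.2% |
| 10% | 9.0% | 0.9% |
| 20% | 16.0% | 3.2% |
| 30% | 21.0% | 6.3% |

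These shares must be multiplied by the proportion of patients whose Week 52 visit is by telehealth, which the documents do not give. If missing weeks cluster within patients, V14 is more often missing too and the shares fall.

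**The case against.** The strongest reply is that this is loose scope and not an error. Section 3.10.3 points back to the weight methods in 3.10.2, while the on-site rules come later. Section 3.11.2 speaks of values taken from the CRF, whereas hunger comes from an e-diary. Section 4.3.5.3 sets the hunger-week rule with no on-site condition. A programmer might never apply the filter to hunger. That is fair as far as it goes, but 3.11.1 covers efficacy data in general, 3.11.2 names both imputation methods, and nothing visible exempts hunger. Read as written, the filter applies.

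The reply on reach is sound. The five model visits are not telehealth-eligible and End of Treatment is in person. One diary entry makes a week evaluable. On-site early termination visits are already admitted.

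A reader might infer more than the documents support:

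- **That telehealth diary weeks are generally thrown away and imputed, or that half the visits are lost.** Six of the seven visits could only backfill predictors, and the seventh matters only when no on-site week is evaluable.
- **That the retrieved-dropout set shrinks and wash-out becomes more likely because patients off treatment prefer telehealth.** No such preference is documented, and Protocol 4.3 encourages these patients to keep attending all regular visits.
- **That every affected value is imputed as missing not at random.** In the wash-out route placebo patients are imputed under MAR. In the retrieved-dropout route non-monotone intermediate gaps are first filled within arm from all observations (SAP 3.10.2).

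**Conclusion.** The point holds in limited form. As written, the SAP lets visit location decide whether an observed home diary week can be used for the hunger endpoint. At the primary timepoint this concerns one visit, Week 52 by telehealth, in patients aged 12 or older with no evaluable on-site week in the window. At the intermediate visits it removes the scheduled fallback for a missing predictor, a smaller matter. By-visit descriptive summaries of observed hunger (SAP 4.3.5.3) carry no on-site condition.

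Neither the number of patients affected nor the direction of any bias can be derived. Telehealth uptake, diary completion, the therapeutic-start definition, the number aged 12 or older and the hunger standard deviation are absent or redacted. The visit mapping assumes scheduled days and a therapeutic start between about Day 22 and Day 50. This is a free improvement and does not threaten the trial's conclusions.

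**What to change.** Add to SAP 3.10.3, with a cross-reference in 3.11: for the daily hunger score, the primary-timepoint window in 3.11.1 and the windows in Table 3-1 accept any scheduled visit, in clinic or telehealth, and the early termination visit, other than bridging visits, provided the preceding diary week is evaluable under 4.3.5.3.

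Apply the same 3.11.1 rule to the Symptoms of Hyperphagia diary, where the filter would otherwise drop an observed value. Table 3-1 should not be extended to it, because SAP 4.3.6 analyses domains without prior imputation as observed. Keep the on-site restriction for weight, BMI, BMI Z-score and BMI P95.

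The cost is a few lines of text and the removal of a visit-type filter for diary data. No new data are needed. The change should be made before unblinding so that it cannot be read as data-driven.

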**3.10.4. Adverse Event Dates**

When tabulating adverse event data, partial dates will be handled as follows:

- If the day of the month is missing, the onset day will be set to the first day of the month unless it is the same month and year as study treatment. In this case, in order to conservatively report the event as treatment-emergent, the onset date will be assumed to be the date of treatment.
- If the onset day and month are both missing, the day and month will be assumed to be January 1, unless the event occurred in the same year as the study treatment. In this case, the event onset will be coded to the day of treatment in order to conservatively report the event as treatment-emergent.
- A missing onset date will be coded as the day of treatment.

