## 6.10. Adverse Events

The definitions of an AE or SAE can be found in [Appendix 5](#). AEs will be recorded from the time a patient provides informed consent/assent. AEs reported after dosing on Day 1 will be considered treatment-emergent AEs (TEAEs).

AE will be reported by the patient (or, when appropriate, by a caregiver, surrogate, or the patient's legally authorized representative).

The Investigator and any designees are responsible for detecting, documenting, and recording events that meet the definition of an AE or SAE and remain responsible for following up AEs that are serious, considered related to the trial treatment or trial procedures, or that caused the patient to discontinue trial treatment (see [Section 4.3](#)).

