### 6.10.1. Time Period and Frequency for Collecting AE and SAE Information

All AEs, including SAEs, will be collected from the provision of informed consent/assent until the SFV at the time points designated in the SoAs ([Table 1](#), [CCI](#)). AEs reported after dosing on Day 1 will be considered TEAEs.

Medical occurrences that begin before the start of trial treatment will be recorded on the Medical History/Current Medical Conditions section of the eCRF (not the AE section).

All SAEs will be recorded and reported to the Sponsor or designee within 24 hours, as indicated in [Appendix 5](#). The Investigator will submit any updated SAE data to the Sponsor within 24 hours of it being available.

Investigators are not obligated to actively seek AE or SAE in former trial patients. However, if the Investigator learns of any SAE, including a death, at any time after a patient has been discharged from the trial, and he/she considers the event to be reasonably related to the trial treatment or trial participation, the Investigator must promptly notify the Sponsor.

The method of recording, evaluating, and assessing causality of AE and SAE and the procedures for completing and transmitting SAE reports are provided in [Appendix 5](#).

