**3.10.5. Concomitant Medication Dates**

While concomitant medication dates will not be directly imputed, partial concomitant start and stop dates will be considered for purposes of identifying prior and/or concomitant status. In general, partial dates with any ambiguity towards prior/concomitant status will be considered concomitant; only partial dates that can clearly indicate prior status will be considered as such.

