##### 4.5.2. Adverse Events

All AEs will be coded using the MedDRA coding system (Version 24.0 or later) and displayed in tables by treatment received and in data listings using system organ class and preferred term. AE grade assessment will be based on investigator reporting using the National Cancer Institute Common Terminology Criteria for Adverse Events (NCI-CTCAE), Version 5.0.

Analyses of AEs will focus on those events that are considered treatment-emergent, where treatment-emergent is defined as any AE with onset after the administration of study medication through the end of the study (14 days after last dose administered), any event that was present at

baseline but worsened in intensity or was subsequently considered drug-related by the Investigator through the end of the study, or any event deemed to be related to study drug exposure.

The number and percentage of pivotal and all patients with any treatment-emergent AE (TEAE), with any TEAE assessed by the Investigator as related to treatment (definite, probable, or possible relationship), with any serious TEAE, with any serious related TEAE, with any TEAE leading to study drug withdrawal, or with any TEAE leading to death will be summarized by treatment received, as needed. The aforementioned summaries will be repeated for Japanese patients, as needed.

The number and percentage of pivotal and all patients with treatment-related TEAEs leading to study discontinuation and non-serious TEAEs will also be summarized by treatment received, as needed.

TEAEs of special interest (Nausea, Vomiting, Diarrhea) will be identified and summarized by treatment received for pivotal and all patients, as needed. A separate summary will be provided for Japanese patients.

In these tabulations, each patient will contribute only once (i.e., the most related occurrence or the most intense occurrence) to each of the incidence rates in the descriptive analysis, regardless of the number of episodes.

All AEs occurring on-study will be listed in patient data listings. Listings will also be provided for the following: drug product related TEAEs, serious TEAEs, drug product related serious TEAEs, TEAEs leading to study drug withdrawal, events of special interest, and deaths.

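### SAP 3.10.4 moves incomplete AE onset dates to the day of treatment without checking the end date, so an event known to have ended before first dose can be tabulated as treatment-emergent

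*SAP*

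**What the plan says.** SAP 3.10.4 has three rules for incomplete AE onset dates.

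- **Day missing.** The onset becomes the first of the month, unless month and year match those of study treatment. In that case, "in order to conservatively report the event as treatment-emergent, the onset date will be assumed to be the date of treatment".
- **Day and month missing.** The onset becomes January 1, unless the year matches that of treatment. In that case, "the event onset will be coded to the day of treatment in order to conservatively report the event as treatment-emergent".
- **Wholly missing.** "A missing onset date will be coded as the day of treatment".

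No rule refers to the AE end date, and no other SAP section adds such a check.

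The main limb of the treatment-emergent definition in SAP 4.5.2 rests on onset: "any AE with onset after the administration of study medication through the end of the study". The other limbs cover worsening of a baseline event and relatedness to study drug. No limb excludes an event because it resolved before dosing.

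On what enters the AE data, Protocol 6.10 says "AEs will be recorded from the time a patient provides informed consent/assent", and Protocol 6.10.1 says "All AEs, including SAEs, will be collected from the provision of informed consent/assent until the SFV". The next paragraph of 6.10.1, however, directs occurrences that begin before treatment starts to the medical history page of the eCRF instead of the AE page.

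For medications, SAP 3.10.5 considers partial start and stop dates. Ambiguous cases count as concomitant, and "only partial dates that can clearly indicate prior status will be considered as such".

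**The concern.** Screening lasts 3 to 8 weeks and AEs are recorded from consent, so the AE dataset can hold events that began and ended before the first dose. If such an event has an incomplete onset, the imputation can override the one date that settles its status. A conservative rule is meant to resolve ambiguity, and a known pre-dose end date leaves none.

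Two things are at stake. An event that cannot be treatment-emergent by onset is counted in the TEAE incidence tables, possibly in the rows for nausea, vomiting and diarrhea, which are the AEs of special interest. The derived record also contradicts itself, because the imputed onset falls after the recorded resolution. The information needed to avoid this is already collected: the AE listing in Protocol 7.6 shows both onset and resolution.

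**Working it through.** The plan states no figure to reproduce here. The check applies the three rules literally to an example, then asks how often the rule acts and what one misclassified patient is worth. The date of treatment is read as the date of first dose.

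**Worked example (assumed dates).** First dose 25 March 2024, true onset 4 March, recorded end 10 March.

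| Onset as recorded | Imputed onset | Treatment-emergent by onset? | Onset after end? |
|---|---|---|---|
| March 2024 | 25 March 2024 | yes | yes, by 15 days |
| 2024 | 25 March 2024 | yes | yes, by 15 days |
| missing | 25 March 2024 | yes | yes, by 15 days |

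If the onset were instead recorded as February 2024, it would be imputed to 1 February and stay pre-treatment. SAP 4.5.2 speaks of onset after administration, so a same-day onset counts through the purpose stated in 3.10.4.

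**How often a pre-dose onset is moved to the first-dose date, given that it is incomplete.** Inputs: screening of 21 to 56 days (SAP 1.3.1). Assumptions: first-dose day uniform over a 365-day year, onset uniform over screening.

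- *Day missing.* The rule acts if onset falls in the month of first dose. With a 30-day month, the mean number of earlier days in that month is (0 + 1 + … + 29)/30 = 14.5. For 56 days of screening, 14.5/56 = 26%. For 21 days, the count is capped at 21: (231 + 8 × 21)/30 = 13.3, and 13.3/21 = 63%. Enumerating a real calendar year gives 26% and 64%.
- *Day and month missing.* The rule acts if onset falls in the year of first dose: 1 − (L + 1)/(2 × 365) for screening length L. For L = 21, 1 − 11/365 = 97%. For L = 56, 1 − 28.5/365 = 92%.
- *Wholly missing.* 100%.

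These shares apply only to pre-dose events with that kind of missing date. They are not shares of all AEs. The documents give no rate of partial AE dates, so the number of affected events cannot be computed.

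**Effect of one misclassified patient.** Planned arms are about 80 and 40 (SAP 3.1). The maximum change in an incidence rate is 1/40 = 2.5 points in placebo or 1/80 = 1.25 points in setmelanotide. Under SAP 4.5.2 each patient contributes once to each rate, so the change is zero if that patient already has a TEAE in the same row.

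**Effect on the between-arm difference.** Suppose a fraction m of patients in each arm is wrongly counted, independently of true TEAE status. A true rate p is then observed as p + (1 − p)m, and the risk difference is multiplied by (1 − m). For an assumed m of 1% to 2%, an assumed true difference of 20 points shrinks by 20 × 0.01 = 0.2 to 20 × 0.02 = 0.4 points.

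**The case against.** The strongest reply is that these records may never reach the AE tables. Protocol 6.10.1 sends an occurrence that begins before treatment to Medical History, and an event that starts and ends in screening is exactly that. If sites follow this sentence, the rule has almost nothing to act on. The point stands as a limit, but it does not close the gap. Protocol 6.10 and the first sentence of 6.10.1 collect AEs from consent, and the Day 1 history update in Protocol 6.4 asks before dosing whether AEs have occurred. The instructions conflict.

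Second, the rule is a declared choice to over-count in preference to missing a TEAE. That is reasonable where status is unknown, but it does not justify overriding a known pre-dose end date. SAP 3.10.5 is not a like-for-like model, since it classifies medications without imputing their dates. It does show the principle of resolving ambiguity one way while respecting dates that settle the matter.

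Third, the by-patient AE listing would let a reader see an anomaly. That is true, but the incidence tables would still carry the event.

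A reader might infer that the rule materially dilutes the setmelanotide–placebo contrast or masks a gastrointestinal signal. The documents do not support that. The size of m is unknown and probably very small, the shrinkage is only the factor (1 − m), and AEs are summarized descriptively. Nor is 26% to 64% a misclassification rate. Misclassification also requires that the event sits on the AE page, that its onset is incomplete, and that its end date proves resolution before dosing.

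**Conclusion.** The gap is real but small. As written, SAP 3.10.4 can class an event known to have ended before first dose as treatment-emergent, with onset after its own resolution. It acts only on incomplete onsets, and a missing day in a month before the treatment month is left pre-treatment. The size is at most 2.5 points (placebo) or 1.25 points (setmelanotide) per misclassified patient in a descriptive table, and zero where the patient already counts in that row. The number of such patients cannot be derived from the documents.

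The conclusion rests on two assumptions: that the date of treatment means the date of first dose, which the SAP does not state although dosing is daily for up to about 60 weeks, and that at least some screening events are entered as AEs. The primary and key secondary analyses, power and alpha are unaffected. This is a desirable refinement and does not threaten the safety conclusions.

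**What to change.** Add to SAP 3.10.4, ahead of the present rules:

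> If the complete or partial AE end date shows that the event ended before the date of first dose, the day-of-treatment imputation is not applied. The onset is set to the first day of the known onset month (or January 1 of the known year), or to the end date if the onset is wholly missing, and in no case later than the end date. The event is not classed as treatment-emergent on the basis of onset. All other incomplete onsets follow the rules below, with date of treatment meaning date of first dose.

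In the worked example the three records would become 1 March 2024, 1 January 2024 and 10 March 2024, none of them treatment-emergent by onset. The worsening and relatedness limbs of SAP 4.5.2 stay as they are. Events with an unknown end date, or one on or after first dose, keep the conservative coding.

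Separately, reconcile the Medical History sentence in Protocol 6.10.1 with AE collection from consent in 6.10, 6.10.1 and 6.4, so that sites record screening events in one place.

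The cost is a short SAP insertion, one programming condition using dates already captured, and a protocol clarification. No conservatism is lost for any event that could have started on treatment.
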